Exclusion criteria	
 Use of the following therapies (within varying protocol defined timeframes): Corticosteroids (oral prednisone) >0.2 mg/kg/day (or greater than the maximum of 15 mg/day for children over 60 kg), anakinra, canakinumab, rilonacept, tocilizumab, TNF inhibitors, abatacept, tofacitinib, rituximab, leflunomide, thalidomide, cyclosporine, intravenous immunoglobulin, 6-Merceptopurine, azathioprine, cyclophosphamide, or chlorambucil, intra-articular, peri-articular or intramuscular corticosteroid injections, any other investigational biologics History of malignancy of any organ system (other than localized basal cell carcinoma of the skin or in-situ cervical cancer), treated or untreated Significant medical diseases, including but not limited to the following: 
 History of organ transplantation Elevated alanine aminotransferase (ALT) ≥ 3x ULN Elevated aspartate aminotransferase (AST) ≥ 3x ULN Increase in total bilirubin defined as per Common Terminology Criteria (CTC) Grade ≥ 2 Serious hepatic disorder (Child-Pugh scores B or C) Chronic Kidney Disease as per NKF stages ≥ 4 Thyroid disease Diagnosis of active peptic ulcer disease Coagulopathy Significant CNS effects including vertigo and dizziness Any conditions or significant medical problems which immunocompromise the patient and/ or places the patient at unacceptable risk for immunomodulatory therapy, e.g. 
 Absolute neutrophil count decreased as per CTC Grade ≥ 1 Thrombocytopenia CTC Grade ≥ 1 Any active or recurrent bacterial, fungal (with exception of onychomycosis) or viral infection

	
 d. HIV infection, Hepatitis B or Hepatitis C infections e. Presence of tuberculosis f. Requirement for administration of antibiotics against latent TB g. Clinical evidence or history of multiple sclerosis or other demyelinating diseases, or Felty's syndrome • Live vaccinations within 3 months prior to the start of the trial, during the trial, and up to 3 months following the last dose
Investigational and reference therapy	
 • Canakinumab • Placebo
Efficacy assessments	
 • PGA • Physician's severity assessment of key disease-specific signs and symptoms • Rescue medication use • Review eDiary instructions • Patient/Parent Global Disease Activity (PPGA) • Auto-Inflammatory Disease Activity Index (AIDAI)

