3.1.1 Screening epoch (Epoch 1)

A screening epoch of up to 12 weeks will be used to assess the eligibility (flare frequency/disease activity periodicity) to one of the three study cohorts, allow patients to achieve significant biologic washout and to taper off non-allowed medications and/ or to achieve a stable regime with the permitted bridging therapies.

Patients will be asked to come fasting for screening and all subsequent visits.

At screening, the investigator will assign a patient to the respective cohort (i.e., TRAPS, HIDS or crFMF), or to the non-randomized groups, and will enter the respective condition into the IRT (Interactive Response Technology). Patients will receive a symptom diary and will be instructed to complete it and contact the site upon the first signs of a disease flare.

Patients who meet all eligibility criteria and who will show a flare during the screening epoch (Epoch 1) will be eligible to enter the randomized treatment epoch (Epoch 2). The date of onset of the flare which will result in randomization (index flare) will be entered on the eCRF.

Patients can be re-screened only once and no study-related re-screening procedure should be performed prior to written re-consent by the subject.

Mis-randomized patients are defined as cases where IRT randomization was performed by the site either prematurely or inappropriately prior to confirmation of the patient's final randomization eligibility and no study medication was administered to the patient. Mis-randomized patients will not be re-screened.

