 - b. Thrombocytopenia as per CTC Grade ≥ 1 : Platelets $< LLN - 75.0 \times 10^9/L$ or below
 - c. Any active or recurrent bacterial, fungal (with exception of onychomycosis) or viral infection
 - d. Presence of Human Immunodeficiency Virus (HIV) infection, Hepatitis B or Hepatitis C infections based on screening lab results
 - e. Clinical evidence or history of multiple sclerosis or other demyelinating diseases, or Felty's syndrome

8. History or evidence of tuberculosis (TB) (active or latent) infection or one of the risk factors TB such as but not limited or exclusive to:
 - a. History of any of the following: residence in a congregate setting (e.g. jail or prison, homeless shelter, or chronic care facility), substance abuse (e.g. injection or non-injection); health-care workers with unprotected exposure to patients who are at high risk of TB or patients with TB disease before the identification and correct airborne precautions of the patient, or
 - b. Close contact (i.e. share the same air space in a household or other enclosed environment for a prolonged period (days or weeks, not minutes or hours)) with a person with active pulmonary TB disease within the last year, or
 - c. Evidence of TB infection (active or latent) determined by positive QuantiFERON (QFT-TB G In-Tube) test or positive Purified Protein Derivative (PPD) test (≥ 5 mm induration) at screening or within 2 months prior to the screening visit, according to the national guidelines. If presence of TB infection (active or latent) is established then treatment for TB as per national guidelines must have been initiated or completed prior to randomization. In the absence of national guidelines, the following has been demonstrated: TB has been treated adequately by antibiotics, cure can be demonstrated and risk factors resulting in TB exposure and contracting have been removed.
9. Administration of any investigational drug or implantation of investigational device, or participation in another trial, within 30 days before screening (*not applicable for patients rolling-over from CACZ885D2203/ CACZ885D2207M*).
10. Live vaccinations within 3 months prior to the start of the trial, during the trial, and up to 3 months following the last dose
11. Donation or loss of blood (amount depending on age and weight, 10-20% or more of volume, within 8 weeks prior to first dosing, or longer if required by local regulation

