5.5.8 Prohibited Treatment

Use of the treatments displayed in [Table 5-1](#) is NOT allowed after Screening.

Table 5-1 Prohibited treatment

Medication	Action to be taken
Corticosteroid maintenance (prednisone equivalent > 0.2 mg/ kg/ day or greater than the maximum of 15 mg/ day for children over 60 kg).	Investigational treatment does not need to be discontinued as a result of this protocol deviation (PD)
Anakinra	Investigational treatment to be discontinued ²
Rilonacept, tocilizumab, rituximab and any other biologics ¹ (investigational or marketed)	Investigational treatment to be discontinued ²
Etanercept, adalimumab, infliximab, or any TNF inhibitor (investigational or marketed)	Investigational treatment to be discontinued ²
Leflunomide, thalidomide, cyclosporine, or i.v. Ig	Investigational treatment to be discontinued ²
Tofacitinib	Investigational treatment to be discontinued ²
6-Mercaptopurine, azathioprine, cyclophosphamide, or chlorambucil	Investigational treatment to be discontinued ²
Intra-articular, peri-articular or intramuscular corticosteroid injections	Investigational treatment to be discontinued ²
Any other investigational non-biological drug	Investigational treatment to be discontinued ²
Any live vaccination ¹	Investigational treatment to be discontinued ²
Treatment for tuberculosis	Investigational treatment to be discontinued

¹ It is recommended not to initiate any live vaccination or biologic treatment until 3 months after the last dose of investigational treatment. Killed or inactivated vaccines may be permitted according to the investigator's discretion.

² Investigational treatments must be permanently discontinued but patient will remain in the study and will be followed-up for safety.

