5.5.9 Discontinuation of study treatment

Patients may voluntarily discontinue investigational treatment for any reason at any time.

The investigator should discontinue investigational treatment for a given patient if, on balance, he/she believes that continuation would be detrimental to the patient's well-being.

Investigational treatment must be discontinued under the following circumstances:

- Emergence of the following adverse events:
 - a. Absolute QTcF > 500 msec, confirmed by repeat ECG measurements

- b. Serious infections combined with neutropenia CTC grades ≥ 1 ($\text{ANC} < 2.0 \times 10^9/\text{L}$)
- c. CKD as per NKF stages ≥ 4 : $\text{eGFR} \leq 29 \text{ mL/min}/1.73 \text{ m}^2$
- d. Confirmed diagnosis of latent or active TB
- e. Onset of any malignancy
- Any of the following laboratory abnormalities:
 - a. Neutropenia CTC Grades ≥ 2 : $\text{ANC} < 1.5 \times 10^9/\text{L}$
 - b. Thrombocytopenia CTC Grade 4: Platelets $< 10.0 \times 10^9/\text{L}$
- Pregnancy
- Use of prohibited treatment as per [Table 5-1](#)
- Any other protocol deviation that results in a significant risk to the patient's safety

The appropriate personnel from the site and Novartis will assess whether investigational treatment should be discontinued for any patient whose treatment code has been broken inadvertently for any reason.

Patients who discontinue investigational treatment should NOT be considered withdrawn from the study. They should return for the assessments indicated by an asterisk (*) in [Table 6-1](#) or [Table 6-2](#). If they fail to return for these assessments for unknown reasons, every effort (e.g. telephone, e-mail, letter) should be made to contact them as specified in [Section 5.5.11](#).

The investigator must also contact the IRT to register the patient's discontinuation from investigational treatment.

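### Exclusion 8c admits patients whose TB treatment has only been started, but Table 5-1 and section 5.5.9 then require study drug to stop

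*Protocol*

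**What the plan says.** **Eligibility (protocol 4.2, exclusion 8c).** The opening of criterion 8 excludes a history or evidence of active or latent TB. Item 8c covers a positive QuantiFERON or PPD test "at screening or within 2 months prior to the screening visit, according to the national guidelines". It then sets conditions for established infection. Where national guidelines exist, "then treatment for TB as per national guidelines must have been initiated or completed prior to randomization". Where they do not, adequate antibiotic treatment must be shown and "cure can be demonstrated and risk factors resulting in TB exposure and contracting have been removed".

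**Prohibited treatment (protocol 5.5.8, Table 5-1).** Use of any listed treatment "is NOT allowed after Screening". One row is "Treatment for tuberculosis", and its action is to discontinue investigational treatment.

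**Mandatory stopping (protocol 5.5.9).** The list of circumstances in which study drug must be stopped includes "Use of prohibited treatment as per" Table 5-1.

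**Protocol summary, exclusion criteria.** The summary excludes the presence of tuberculosis and, separately, "Requirement for administration of antibiotics against latent TB".

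**The concern.** In 8c, starting treatment is offered as an alternative to completing it. A patient part-way through a course at Day 1 is therefore acceptable on the national-guideline route, yet from that day the same patient is using a prohibited treatment. One rule admits the patient and another takes the patient off study drug.

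Sites are likely to handle this differently. Some will randomize, some will screen-fail, and some may randomize and overlook the prohibition. A patient who is dosed and then stopped may contribute no efficacy data, because section 6.4 waives efficacy assessments for patients whose treatment must be permanently discontinued. Day 15 and Week 16 results could then be missing. Each cohort plans only 60 randomized patients, 30 per arm (protocol section 4), so avoidable losses are worth preventing.

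**Working it through.** The main check is textual. Take one patient with established latent TB who starts guideline treatment during screening and is still taking it at Day 1.

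| Text | Result for this patient |
|---|---|
| 4.2, opening of criterion 8 | Excluded if read alone |
| 4.2, 8c, national guidelines exist | Accepted, because treatment has been initiated |
| 4.2, 8c, no national guidelines | Not accepted, because cure must be demonstrated |
| Summary exclusion criteria | Excluded, because antibiotics against latent TB are required |
| 5.5.8, Table 5-1 | Using a prohibited treatment after Screening |
| 5.5.9 | Study drug must be discontinued |

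**Is there an exemption?** None appears in the TB row, the table footnotes, section 5.5.9 or the TB assessments in section 6.2.1. The corticosteroid row of Table 5-1 says that study drug need not be stopped, so a waiver was written where one was wanted.

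**Could the ban mean only newly started treatment?** Section 5.5.8 bars use. Footnote 1 of the same table speaks of initiating a treatment when starting is what it means. The ban therefore covers a course already under way.

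**Could study drug be paused?** Section 5.5.5 permits no interruptions.

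**Which patients are affected?** Only those on the national-guideline route with unfinished treatment. Active TB would ordinarily be excluded by criterion 7c (active infection), so the realistic case is latent TB.

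**Can a course still be running at Day 1?** Inputs from the documents:

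- Section 3.1.1: "A screening epoch of up to 12 weeks will be used to assess the eligibility"; Table 6-1 gives Day -84 to -3.
- Exclusion 8c: tests up to 2 months before the screening visit count, taken here as 61 days.

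Longest time from test to Day 1:

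- Test at the screening visit: 84 days / 7 = 12.0 weeks.
- Earliest test in the look-back: 84 + 61 = 145 days; 145 / 7 = 20.7 weeks.

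For a course of L weeks started at the test, the treatment left at Day 1 is at least max(0, L - 12.0) or max(0, L - 20.7) weeks. Course length is not in the documents, so L is an assumed range.

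| Assumed L (weeks) | Left at Day 1, started at Day -84 | Left at Day 1, started 61 days earlier |
|---|---|---|
| 12 | 0 | 0 |
| 16 | 4 | 0 |
| 24 | 12 | 3.3 |
| 36 | 24 | 15.3 |

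These are minimum values, since a shorter screening period leaves more. For comparison, Epoch 2 lasts 16 weeks.

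**The case against.** **The patient is excluded anyway.** Any single exclusion criterion is enough, the opening of criterion 8 bars a history of TB, and the summary bars patients who need latent-TB antibiotics. Item 8c never says the patient becomes eligible, whereas 6b and 6c do say so for repeat liver tests. A careful site might therefore screen-fail the patient. This has some force, but if the opening were absolute, the sentence about initiated or completed treatment and the cure condition would have no function. They make sense only as conditions for acceptance. Section 4.2 also forbids investigators to add exclusions of their own.

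**The loss of data is not certain.** The TB row is the only row requiring discontinuation that lacks the footnote making it permanent, and section 6.4 waives efficacy assessments only for permanent discontinuation. The glossary definition of treatment discontinuation and section 5.5.5 point towards permanence, but the point is arguable. A site that notices the ban at Baseline may never give a dose, and the patient then falls outside the full analysis set. For a dosed patient, the non-responder rule (protocol 9.4.3, SAP 1.10.1.3) covers those who leave the study. Section 5.5.9 says that stopping drug is not withdrawal, so the rule does not expressly cover this patient. Missing data are thus a possible consequence, not a certain one.

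**The group is small.** Under section 6.2.1.2 a PPD-positive patient with a negative confirmatory test is eligible without further work-up, and with short courses nothing remains at Day 1. Both points stand, and they limit the size of the problem.

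**Completed treatment may conflict too.** If Screening means Visit 1, a course that ends between Visit 1 and Day 1 breaches section 5.5.8. No study drug has been given by then, so there is none to discontinue.

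**Conclusion.** The inconsistency is real, and it lies in 8c's acceptance of treatment that has merely been initiated. Completed treatment and the cure route do not lead to study drug being stopped. The conclusion rests on reading the 8c sentence as a condition for acceptance, which is the reading that gives it a purpose.

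The effect is minor: a few patients at most who could be randomized and then have to stop, and uneven practice between sites. The documents give no count. How often a course overlaps Day 1 depends on course length, which is assumed here. No effect on type I error or bias between arms is claimed, because eligibility does not depend on arm.

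**What to change.** In exclusion 8c, delete the option of treatment having only been initiated, so that the national-guideline route requires completion before randomization. This agrees with the summary, the cure condition and Table 5-1.

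The cost is one wording change in the next amendment. A few patients on latent-TB treatment become ineligible until they finish the course; section 3.1.1 allows one re-screening.

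If the sponsor does want patients on treatment in the trial, more edits are needed:

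- exempt courses begun under 8c from Table 5-1 and from the prohibited-treatment item in 5.5.9;
- remove the summary exclusion on latent-TB antibiotics;
- reword the opening of criterion 8;
- make clear that the 5.5.9 item on confirmed latent or active TB does not apply to infection already established at screening, since TB status is re-tested at Day 281 and Day 785 (section 6.2.1).

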5.1 Protocol requested treatment

5.1.1 Investigational treatment

Novartis will provide the following investigational treatment:

- 1. Canakinumab solution for injection in vial which contains 150 mg/mL canakinumab in 1 mL solution
- 2. Placebo matching the canakinumab solution.

5.1.2 Additional study treatment

No additional treatment beyond investigational treatment is requested for this trial.

5.2 Treatment arms

In the randomized treatment epoch (Epoch 2), patients in each cohort will be assigned to one of the following 2 treatment arms in a ratio of 1:1 at Baseline:

- 1. Canakinumab 150 mg (or 2 mg/kg for patients weighing ≤ 40 kg) q4w
- 2. Placebo

Patients who will be eligible for blinded escape (see [Section 3.1.2.2](#)) will receive a single add-on injection of canakinumab (150 mg [or 2 mg/kg for patients weighing ≤ 40 kg]) from Day 8 to Day 28. Patients will then receive below treatment until investigational treatment discontinuation (TD)/ premature subject withdrawal (PSW):

1. Patients randomized to canakinumab 150 mg q4w will switch to canakinumab 300 mg (or 4 mg/kg for patients weighing ≤ 40 kg) q4w
2. Patients randomized to placebo switch to canakinumab 150 mg (or 2 mg/kg for patients weighing ≤ 40 kg) q4w

Patients who require additional up-titration (open-label treatment arm as detailed in [Section 3.1.2.3](#)) will switch to canakinumab 300 mg s.c. (or 4 mg/kg for patients weighing ≤ 40 kg) q4w.

In the randomized withdrawal epoch (Epoch 3), responders to canakinumab 150 mg (or 2 mg/kg for patients weighing ≤ 40 kg) q4w (see [Section 3.1.3](#) for details) will be re-randomized on Day 113 in a ratio of 1:1 to:

1. Canakinumab 150 mg (or 2 mg/kg for patients weighing ≤ 40 kg) q8w
2. Placebo

Patients who required up-titration during Epoch 2 will start their participation in Epoch 3 in the open-label treatment arm (canakinumab 150 mg (or 2 mg/kg for patients weighing ≤ 40 kg) q8w or canakinumab 300 mg (or 4 mg/kg for patients weighing ≤ 40 kg) q8w. Any up-titration in case of lack of therapeutic effect will be allowed as outlined in [Section 3.1.3.2](#).

Patients from the non-randomized group (patients > 28 days but < 2 years old) and Japanese crFMF patients with non-exon 10 mutations) entering the study at Epoch 2 will receive open-label canakinumab 150 mg (or 2 mg/kg for patients weighing ≤ 40 kg) q4w.

TRAPS patients previously participating in CACZ885D2203 or CACZ885D2207M entering the study at the beginning of Epoch 3 will be assigned to the open-label treatment arm at a dose of canakinumab 150 mg (or 2 mg/kg for patients weighing ≤ 40 kg) q8w or canakinumab 300 mg (or 4 mg/kg for patients weighing ≤ 40 kg) q8w.

Open-label treatment in Epoch 4 will be handled as detailed in [Section 3.1.4](#).

5.3 Treatment assignment, randomization

At Baseline, all eligible patients within each cohort will be randomized via Interactive Response Technology (IRT) to one of the treatment arms. The investigator or his/ her delegate will contact the IRT after confirming that the patient fulfills all the inclusion/ exclusion criteria. The IRT will assign a randomization number to the patient, which will be used to link the patient to a treatment arm and will specify a unique medication number for the first package of investigational treatment to be dispensed to the patient. The randomization number will not be communicated to the caller.

At the beginning of the randomized withdrawal epoch (Epoch 3), all eligible patients within each cohort will be re-randomized via Interactive Response Technology (IRT) to one of the treatment arms. The investigator or his/ her delegate will contact the IRT after confirming that the patient qualifies for entering the withdrawal epoch.

The randomization numbers will be generated using the following procedure to ensure that treatment assignment is unbiased and concealed from patients and investigator staff. A patient randomization list will be produced by the IRT provider using a validated system that

automates the random assignment of patient numbers to randomization numbers. [REDACTED]

Randomization will be stratified by disease cohort. [REDACTED]

Patients from the non-randomized cohort and roll-over TRAPS patients will be assigned to the open-label treatment in Epoch 2 and Epoch 3 respectively via IRT.

In case of add-on injection from Day 8 to Day 28, IRT will assign a unique medication number for blinded administration. At the next scheduled visit, the new dosing regimen will be initiated by IRT automatically and medication number assigned accordingly.

In case of up-titration from Day 29 onwards, the new dosing regimen will be initiated by IRT automatically at the next scheduled visit (including Day 29 visit) and medication number assigned accordingly.

5.4 Treatment blinding

Patients, investigator staff, persons performing the assessments, and data analysts will remain blind to the identity of the randomized or re-randomized treatment assignment from the time of randomization until database lock, using the following methods:

1. Randomization data are kept strictly confidential until the time of unblinding, and will not be accessible by anyone else involved in the study with the following exceptions:
 - a. Unblinded lab personnel charged with conducting the PD/ PK and/ or IG assays.
2. The identity of the treatments will be concealed by the use of investigational treatment that are all identical in packaging, labeling, schedule of administration, appearance.

Unblinding will only occur for placebo responders at the end of the randomized treatment epoch (Epoch 2), in the case of patient emergencies (see [Section 5.5.12](#)), in case of an interim analysis (see [Section 9.6](#)) and at the conclusion of the study.

The randomization codes associated with patients from whom PK samples are taken will be disclosed to PK analysts who will keep PK results confidential until data base lock.

